### **10.5.5** Baseline Descriptive Statistics

Baseline demographic characteristics will be reported.

## 10.5.6 Planned Interim Analyses

As indicated in the two-stage design, the number of responses after 12 evaluable participants have been treated will be noted and will be used to determine if enrollment to the second stage of accrual may continue.

## 10.5.7 Sub-Group Analyses

None.

Version Date: 7/10/2025

## 10.5.8 Tabulation of individual Participant Data

None.

## 10.5.9 Exploratory Analyses

The following are the planned exploratory analyses:

- Utilize participant blood and biopsy tissue acquired on this protocol to identify factors that
  may be important in determining participant response to treatment (techniques involved
  immune phenotyping analysis, whole genome sequencing, ATAC-seq, Digital Spatial
  Profiling (Nanostring GeoM) and effect of the study drug on tumor a circulating cell
  populations.
- Evaluate ctDNA as a marker of response in ASCP

The exploratory objectives are intended to collect data for use in planning future scientific investigations or clinical research. These analyses are expected to be performed first using descriptive techniques, reporting descriptive statistics including confidence intervals when appropriate. Any statistical tests performed for evaluation of exploratory objectives will be done without formal adjustment for multiple comparisons, but in the context of the number of tests performed.

#### 11 COLLABORATIVE AGREEMENTS

#### 11.1 AGREEMENT TYPE

Clinical trial agreement (CTA # 01208-21) with Minneamrita is executed.

#### 12 HUMAN SUBJECTS PROTECTIONS

## 12.1 RATIONALE FOR SUBJECT SELECTION

All participants meeting the criteria listed in Section 2.1 are eligible for enrollment regardless of race, ethnicity, sex, nationality, or English-language ability.

Participants with ASCP are specifically being recruited to this study because the preclinical evidence supports efficacy of the trial intervention in this participant population.

## 12.2 PARTICIPATION OF CHILDREN

ASCP is typically a disease of adults. Because ASCP does not typically occur in children and no dosing or adverse event data are currently available on the use of Minnelide in participants <18 years of age, children are excluded from this study.

### 12.3 RISK/BENEFIT ASSESSMENT

### 12.3.1 Known Potential Risks

### 12.3.1.1 Minnelide

Minnelide given in oral form is still under investigation. At this stage, the major treatment-related toxicities appear to be related to myelosuppression, including neutropenia, febrile neutropenia and neutropenic sepsis. At least one death due to sepsis attributed to Minnelide has been reported on studies of IV and oral Minnelide.

Version Date: 7/10/2025

#### 12.3.1.2 Blood Collection

Side effects of blood draws include pain and bruising, lightheadedness, and rarely, fainting. Up to 60.5 mL of research blood may be collected at any visit but no more than 178 ml in an 8 week period.

### 12.3.1.3 Urine Collection

No physical risks are associated with urine collection.

## 12.3.1.4 Electrocardiogram

Some skin irritation can occur where the ECG/EKG electrodes are placed. The test is completely painless, and generally takes less than a minute to perform.

## 12.3.1.5 Imaging

In addition to the radiation risks discussed below, CT scans may include the risks of an allergic reaction to the contrast. Participants might experience hives, itching, headache, difficulty breathing, increased heartrate and swelling. Furthermore, the IV catheter used to administer the contrast may cause bleeding, infection or inflammation of the skin and vein with pain and swelling. Participants undergoing gadolinium enhanced MRIs may also be at risk for kidney damage. MRIs include the additional risk of damage to hearing.

## 12.3.1.6 Biopsy Collection

The risks of the optional research biopsies include pain, bleeding and infection at the biopsy site. In addition, as the biopsies may be collected under CT guidance, participants in this study may be exposed to radiation as discussed below.

### 12.3.1.7 Risks from Radiation Exposure

On this study, patients will receive up to 3 CT-guided biopsies and up to 5 CT scans. The total radiation dose for research purposes will be approximately 8.9 rem. The risk of getting cancer from the radiation exposure in this study is 0.9% and of getting a fatal cancer is 0.4%.

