- Hepatitis testing: HBsAg and HCV RNA (qualitative) if not performed in the last 3 months
- Pregnancy test: Serum β-HCG pregnancy test for women of child-bearing potential
- 2.3.2.6 Electrocardiogram (ECG)
- 2.3.2.7 Imaging scans: Computed tomography (CT) / magnetic resonance imaging (MRI) scan as clinically indicated to document disease status (including chest, abdomen, pelvis, and other regions as clinically indicated). In addition, a brain scan may be required to exclude brain metastases if clinically indicated by participant history or exam.
- 2.3.2.8 Concomitant medications: review to include notation of all medications taken within 30 days prior to treatment initiation

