#### 3 STUDY IMPLEMENTATION

#### 3.1 STUDY DESIGN

This is a Phase II single arm, single cohort study that will enroll up to 25 evaluable participants with advanced ASCP that has been previously treated. In order to account for screen failures and inevaluable patients (i.e., participants who are not evaluable for the primary endpoint of response), the accrual ceiling will be set at 55 participants.

Accrual may continue up to 15 treated participants while the primary objective is being determined but no new participants may be accrued once it is known that this criteria has not been met (see Sections 10.3 and 10.5.6).

Initial participants will self-administer Minnelide at 2 mg PO daily on Days 1-21 of each 28 days cycle. Those joining the study after modification dated 3/10/23 will receive Minnelide at 2.5 mg PO daily on Days 1-21 of each 28 days cycle. Participants initially enrolled at the 2 mg dose may be increased to the 2.5 mg dose at the discretion of the study team if they have been tolerating the lower dose (i.e., intrapatient dose escalation is permitted). Treatment will continue for up to 12 cycles (1 year) in the absence of disease progression or unacceptable toxicity. After initiation of treatment, restaging scans will be conducted approximately every 2 cycles or 8 weeks. Optional biopsies will be requested mid-cycle 1 and at time of progression.

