- Symptom assessment: verbal review of participant's current symptoms
- Physical exam, including vital signs and weight: review of organ systems, weight (kg), and vital signs (i.e., temperature, pulse, respirations, blood pressure). After initiation of study drug, symptom-directed physical examinations will be performed as clinically indicated in the investigator's judgment.
- Performance status (ECOG): an assessment of activities of daily living; see **Appendix A: Performance Status Criteria**
- Clinical laboratories:
  - CBC with differential: includes Neutrophils, Lymphocytes, Monocytes, Eosinophils, Basophils, WBC, RBC, Hemoglobin, Hematocrit, MCV, RDW, Platelet
  - Serum Chemistries: Sodium (NA), Potassium (K), Chloride (CL) Total CO2 (Bicarbonate), Creatinine, Glucose, Urea nitrogen, Alkaline Phosphatase, ALT/GPT, AST/GOT, Total Bilirubin, Direct Bilirubin, Albumin, Calcium, Magnesium, Phosphorus
  - o Urinalysis: protein, specific gravity, glucose, and blood
  - o Pregnancy test: Serum β-HCG for women of child-bearing potential
  - Serum tumor markers: CA19-9 and CEA (or CA-125 if not a secretor of CA19-9 and CEA)
- Imaging scans: CT scans or MRI as required for evaluation (including chest, abdomen, pelvis, and other regions as clinically indicated); may be adjusted to assess additional known sites of disease, as needed. Performed up to 3 days prior to start of every other cycle (typically odd numbered cycles). If radiologic response to treatment is observed (see Section 6.3), confirmatory scans may be performed at 4 week interval (e.g., start of next cycle), and in this case subsequent scans should continue prior to every other cycle thereafter (i.e., prior to even numbered cycles).
- Adverse events and Concomitant medication review: Adverse events (assessed using the NCI CTCAE v5.0) and concomitant medication will be continuously monitored throughout the study until 30 days from last dose of Minnelide or start of new anticancer treatment, whichever comes first. Adverse events that occur beyond 30 days after the last administration will be recorded as noted in Section 6.1.
- Minnelide administration, including dispensing and adherence review: Study drug will be dispensed at each cycle and instructed to be self-administered by participants per schedule-see Section 3.2. Participants will be given a dosing diary (see Appendix B: Participant Medication Diary); to be reviewed at each noted visit for drug adherence/accountability.

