#### 3.5 END OF TREATMENT ASSESSMENTS

The participant will continue on study drug until there is evidence of tumor progression, intolerable toxicities, completion of 12 cycles, or withdraws from treatment (refer to Section 3.9.1). The "End of Treatment" assessments (Section 3.7) will be performed 7-35 days after completing the last dose of study drug or before the initiation of a new anti-cancer treatment, whichever comes first. If the participant cannot return to the study center for this visit, the participant may complete assessments locally, including seeing a local physician for a physical exam and local clinical laboratories, and the study team will follow-up with the participant remotely. Imaging scans need only be performed at end of treatment, if not performed within the last 4 weeks.

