#### 6.3 RESPONSE CRITERIA

For the purposes of this study, participants should be re-evaluated for response every 8 weeks. In addition to a baseline scan, confirmatory scans should also be obtained 4-8 weeks (not less than 4) weeks following initial documentation of objective response.

Response and progression will be evaluated in this study using the new international criteria proposed by the revised Response Evaluation Criteria in Solid Tumors (RECIST) guideline version 1.1 (22). Changes in the largest diameter (unidimensional measurement) of the tumor lesions and the shortest diameter in the case of malignant lymph nodes are used in the RECIST criteria.

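### The radiation section states a maximum of 5 CT scans, but the protocol's own schedule allows 7, or 8 with a confirmatory scan, so the dose and risk figures need a stated scope or a recalculation

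*Combined protocol and SAP*

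**What the plan says.** Section 12.3.1.7 makes three statements:

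- Procedures: "On this study, patients will receive up to 3 CT-guided biopsies and up to 5 CT scans".
- Dose: "The total radiation dose for research purposes will be approximately 8.9 rem".
- Risk: "The risk of getting cancer from the radiation exposure in this study is 0.9% and of getting a fatal cancer is 0.4" (the last figure is also a percentage).

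The imaging schedule is set elsewhere:

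- Section 3.1: "Treatment will continue for up to 12 cycles (1 year) in the absence of disease progression or unacceptable toxicity".
- Section 2.3.2.7 (screening): a CT or MRI "scan as clinically indicated to document disease status".
- Section 3.4 (on treatment): "Performed up to 3 days prior to start of every other cycle (typically odd numbered cycles". If a response is seen, a confirmatory scan may follow at 4 weeks, and later scans then move to even-numbered cycles.
- Section 6.3: "confirmatory scans should also be obtained 4-8 weeks (not less than 4) weeks following initial documentation of objective response".
- Section 3.5: "Imaging scans need only be performed at end of treatment, if not performed within the last 4 weeks". The visit falls 7 to 35 days after the last dose, or before a new anti-cancer treatment if that comes first.
- The calendar in section 3.7 marks imaging at screening, at every other cycle and at the end-of-treatment visit.

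**The concern.** A figure introduced by the words up to is a maximum, and the schedule goes past it. The figure matters because the dose and the two cancer risks are presented alongside it as the participant's exposure. A maximum that is too small is wrong first for participants who stay on treatment longest and for responders, since they have the most scans. The three sentences also differ in scope: procedures on this study, dose for research purposes, and risk from exposure in this study. A reader cannot tell whether some scheduled scans were left out on purpose.

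**Working it through.** **The plan's own figures.** Scans before Cycles 3, 5, 7, 9 and 11 number 5, so the stated count equals the on-treatment restaging scans alone, without confirmation. The 8.9 rem cannot be reproduced, because no dose per scan or per biopsy is given.

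**Is an end-of-treatment scan due after 12 cycles?** With 28-day cycles, Day 1 of Cycle k is study day 28(k − 1) + 1.

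- Cycle 11 Day 1: 28 × 10 + 1 = day 281.
- Cycle 12 Day 1: 28 × 11 + 1 = day 309.
- Last dose (Cycle 12 Day 21): 309 + 20 = day 329.
- End-of-treatment visit: 329 + 7 = day 336 to 329 + 35 = day 364.
- The Cycle 11 scan is on days 278 to 281 (up to 3 days before). The gap to the visit is 336 − 281 = 55 to 364 − 278 = 86 days.

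Both gaps exceed 4 weeks, so the scan is due.

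**Count without a confirmatory scan:** 1 screening + 5 on treatment + 1 end of treatment = 7.

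**Count with a 4-week confirmatory scan.** Whichever scan first shows response, there are 6 on-treatment scans:

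| First response at | Scans before cycles | Number |
|---|---|---|
| Cycle 3 | 3, 4, 6, 8, 10, 12 | 6 |
| Cycle 5 | 3, 5, 6, 8, 10, 12 | 6 |
| Cycle 7 | 3, 5, 7, 8, 10, 12 | 6 |
| Cycle 9 | 3, 5, 7, 9, 10, 12 | 6 |
| Cycle 11 | 3, 5, 7, 9, 11, 12 | 6 |

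The Cycle 12 scan (days 306 to 309) is 336 − 309 = 27 to 364 − 306 = 58 days before the visit. An end-of-treatment scan is therefore due unless the visit falls at the very start of its window or is brought forward by a new treatment. The total is 1 + 6 + 1 = 8, or 7 in that exception.

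**Dose.** Let c be the dose per CT scan and b the dose per CT-guided biopsy. Assume the 8.9 rem covers exactly the 5 scans and 3 biopsies named:

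3b + 5c = 8.9, so c ≤ 8.9 / 5 = 1.78 rem.

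With n scans the dose is 8.9 + (n − 5)c. Risk is scaled linearly (an assumption): 0.9 / 8.9 = 0.101 and 0.4 / 8.9 = 0.045 percentage points per rem. The values of c below are illustrative; only the last, the limit, follows from the documents.

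| c (rem) | b (rem) | 7 scans: rem; any / fatal | 8 scans: rem; any / fatal |
|---|---|---|---|
| 0.5 | 2.13 | 9.9; 1.00% / 0.44% | 10.4; 1.05% / 0.47% |
| 1.0 | 1.30 | 10.9; 1.10% / 0.49% | 11.9; 1.20% / 0.53% |
| 1.5 | 0.47 | 11.9; 1.20% / 0.53% | 13.4; 1.36% / 0.60% |
| 1.78 (limit) | 0 | 12.5; 1.26% / 0.56% | 14.2; 1.44% / 0.64% |

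The last row gives the biopsies no dose at all, so it is a bound and not an estimate. If only on-treatment scans count and one is confirmatory, the bound is 8.9 + 1.78 = 10.7 rem.

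**The case against.** The strongest reply is that the dose sentence is limited to research purposes. Five is exactly the number of restaging scans, so the screening and end-of-treatment scans may have been treated as clinical care. The screening scan is worded as clinically indicated and may come from an outside facility or another protocol. The end-of-treatment scan is conditional: a participant who stops when a scheduled scan shows progression will often need none. Section 3.4 makes the 4-week confirmatory scan optional, and section 6.3 allows up to 8 weeks, so the next restaging scan can serve. MRI may replace CT throughout. Section 12.3.3 puts median survival at no more than 3 months, so few participants may reach the maximum, and no endpoint or analysis depends on it.

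Much of this stands. It rules out the stronger reading that a reader might infer, namely that 8.9 rem and 0.9% / 0.4% are shown to be too low. If the extra scans were excluded on purpose, the dose may be right for what it covers.

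It does not rescue the count. Only the dose sentence carries the research limit; the count and risk sentences refer to the study. No section names an excluded scan. Even on the narrowest reading, on-treatment scans only, a responder confirmed at 4 weeks has 6. MRI is permitted, but nothing caps CT at 5, and a maximum has to cover the participant imaged by CT throughout.

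**Conclusion.** Wrong as written. The stated maximum of 5 CT scans contradicts the schedule. With all imaging by CT and 12 completed 28-day cycles, the count is 7, and up to 8 with a 4-week confirmatory scan.

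The consequence for dose and risk is conditional: they are understated unless the extra scans are deliberately excluded as standard care, which the section does not say. If all scheduled scans count, the upper limits are about 12.5 rem and 1.3% / 0.56% for 7 scans, and 14.2 rem and 1.4% / 0.64% for 8. These rest on 8.9 rem covering 5 scans and 3 biopsies, and on linear scaling of risk. The documents support no specific percentage increase, because the split of dose between scans and biopsies is unknown.

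A reader might also infer that the consent form is wrong. Its pages are not among the material reviewed, so it can only be checked. The point concerns participant-risk information and leaves the primary analysis untouched.

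**What to change.** In section 12.3.1.7:

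1. Recount the maximum number of CT scans from sections 2.3.2.7, 3.4, 3.5, 3.7 and 6.3, including the confirmatory scan.
2. State which scans count as research exposure and, if any are excluded as standard care, name them and give the reason.
3. Use the same scope for the count, dose and risk sentences.
4. Give the dose per CT scan and per CT-guided biopsy, and recalculate the total and both risks for the stated count.
5. Check that the consent carries the same figures.

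The cost is a radiation-safety recalculation and a text amendment. If the extra scans are included, the stated risk becomes slightly less favourable. Design, endpoints and the imaging schedule need not change.

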### 12.3.2 Known Potential Benefits

Pre-clinical studies of Minnelide in ASCP models support our hypothesis that participant tumors will be sensitive to this drug. Better control of ASCP provided by Minnelide may improve tumor-related symptoms such as pain and fatigue and may slow disease progression. Treatment with these drugs have the potential to provide direct benefit to participants.

### 12.3.3 Assessment of Potential Risks and Benefits

Advanced ASCP that has progressed after previous treatment has a grim prognosis with median survival of no more than 3 months. There are no standard treatments for this disease. Available research suggests that Minnelide may be effective against ASCP. These potential benefits are balanced against the risk of drug toxicity. While Minnelide can cause serious toxicities, these toxicities have been successfully managed with supportive measures and dose reduction in other clinical studies. In addition, the frequent clinical and laboratory assessments that have been built into this protocol will further minimize risk to participants.

Version Date: 7/10/2025

#### 12.4 Consent Process and Documentation

The informed consent document will be provided as a physical or electronic document to the participant for review prior to consenting. A designated study investigator\* will carefully explain the procedures and tests involved in this study, and the associated risks, discomforts and benefits. In order to minimize potential coercion, as much time as is needed to review the document will be given, including an opportunity to discuss it with friends, family members and/or other advisors, and to ask questions of any designated study investigator. A signed informed consent document will be obtained prior to entry onto the study.

The initial consent process as well as re-consent, when required, may take place in person or remotely (e.g., via telephone or other NIH approved remote platforms used in compliance with policy, including HRPP Policy 303) per discretion of the designated study investigator and with the agreement of the participant. Whether in person or remote, the privacy of the participants will be maintained. Consenting investigators (and participant, when in person) will be located in a private area (e.g., clinic consult room). When consent is conducted remotely, the participant will be informed of the private nature of the discussion and will be encouraged to relocate to a more private setting if needed.

Consent will be documented with required signatures on the physical document (which includes the printout of an electronic document sent to participant) or as described below, with a manual (non-electronic) signature on the electronic document. When required, witness signature will be obtained similarly as described for the investigator and participant.

## Manual (non-electronic) signature on electronic document:

When a manual signature on an electronic document is used for the documentation of consent at the NIH Clinical Center, this study will use the following to obtain the required signatures:

- Adobe platform (which is not 21 CFR Part 11 compliant); or,
- iMedConsent platform (which is 21 CFR Part 11 compliant)

During the consent process, participants and investigators will view individual copies of the approved consent document on screens at their respective locations (if remote consent); the same screen may be used when in the same location but is not required.

Both the investigator and the participant will sign the document using a finger, stylus or mouse.

Note: Refer to the CCR SOP PM-2, Obtaining and Documenting the Informed Consent Process for additional information (e.g., verification of participant identity when obtaining consent remotely) found at: https://nih.sharepoint.com/sites/NCI-CCR-OCD-Communications/SitePages/OEC-Administrative---Clinical-Research-(ADCR).aspx?Mode=Edit.

## 13 REGULATORY AND OPERATIONAL CONSIDERATIONS

### 13.1 STUDY DISCONTINUATION AND CLOSURE

This study may be temporarily suspended or prematurely terminated if there is sufficient reasonable cause. Written notification, documenting the reason for study suspension or termination, will be provided by the suspending or terminating party to study participants, investigator, funding agency, the Investigational New Drug (IND) sponsor and regulatory authorities. If the study is prematurely terminated or suspended, the Principal Investigator (PI) will promptly inform study participants, the Institutional Review Board (IRB), and sponsor and

Version Date: 7/10/2025

will provide the reason(s) for the termination or suspension. Study participants will be contacted, as applicable, and be informed of changes to study visit schedule.

Circumstances that may warrant termination or suspension include, but are not limited to:

- Determination of unexpected, significant, or unacceptable risk to participants
- Demonstration of efficacy that would warrant stopping
- Insufficient compliance to protocol requirements
- Data that are not sufficiently complete and/or evaluable
- Determination that the primary endpoint has been met
- Determination of futility

Study may resume once concerns about safety, protocol compliance, and data quality are addressed, and satisfy the sponsor, IRB and as applicable, Food and Drug Administration (FDA).

## 13.2 QUALITY ASSURANCE AND QUALITY CONTROL

The clinical site will perform internal quality management of study conduct, data and biological specimen collection, documentation and completion. An individualized quality management plan will be developed to describe a site's quality management.

Quality control (QC) procedures will be implemented beginning with the data entry system and data QC checks that will be run on the database will be generated. Any missing data or data anomalies will be communicated to the site(s) for clarification/resolution.

Following written Standard Operating Procedures (SOPs), the monitors will verify that the clinical trial is conducted and data are generated and biological specimens are collected, documented (recorded), and reported in compliance with the protocol, International Council for Harmonisation Good Clinical Practice (ICH GCP), and applicable regulatory requirements (e.g., Good Laboratory Practices (GLP), Good Manufacturing Practices (GMP)).

The investigational site will provide direct access to all trial related sites, source data/documents, and reports for the purpose of monitoring and auditing by the sponsor, and inspection by local and regulatory authorities.

